- 1. Sociodemographic: a brief baseline survey will be administered to collect a minimal amount of information. Additional study relevant information (only for enrolled patients) will be collected to enable study analyses.
- 2. Laboratory assessments and other clinical assessments: patients will only be monitored according to their physicians' standard practice without additional study-specified interventions and evaluations. Only available assessments will be collected from routine testing/evaluations using electronic approaches.
- 3. Assessments may not be conducted at the exact scheduled time intervals as there will be no intervention for patients' clinical care. Only available assessments will be collected from routine testing/evaluations. The schedule is to remind physicians to collect data regularly.
- 4. Adverse event and pregnancy exposure reporting: only spontaneous AEs/SAEs and pregnancy exposure related to any GSK products will be reported and summarized.
- 5. The baseline assessment filling with grey colure is mandatory and requested for baseline data collection.
- 6. Follow-up data collection period (e.g. months 6, 12, 18, 24, 30, 36) for patients who have started TDF before the entry of study will be anchored to their actual TDF initiation dates.

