5. STUDY DESIGN

5.1. Overall Design

This is a China-based multi-center, prospective, longitudinal, real-world study, taking a naturalistic approach, capturing real-world medical practice and patient outcomes using a non-interventional design. Patients with diagnosed CHB who newly initiate and continue TDF monotherapy or combination therapy will be consecutively recruited from general and specialized hospitals across China. Site/hospital selection will consider geographic and hospital type/tier representativeness, investigators' research interest, as well as feasibility such as electronic data collection approaches. For non-enrolled subjects, reasons of exclusion will be collected.

During the study, patients will seek and receive medical care as they do in regular clinical practice setting without investigational product tested. Specifically, patients' diagnosis, treatment, and monitoring will be left to their physicians' routine practice without study-

dictated visits and procedures. Minimal patient evaluations will be done by physicians, e.g. baseline patient demographics and clinical characteristics and patients' treatment adherence. Minimal lab tests in line with routine clinical practice (HBV DNA, serum creatinine, and serum phosphate) will be conducted in a central lab on the basis of the judgement of treating physicians and willingness of patients.

Other patient data will be collected using electronic approaches, mainly from lab test reports or medical records at the entry of this study and thereafter at 6-month intervals for 3 years. As this is a real-world study without mandatory scheduled visits, patients may not seek medical care and conduct assessments (e.g. lab tests) exactly at 6-month intervals. The 6-month interval is set to remind investigators to collect data regularly.

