7. STUDY ASSESSMENTS AND PROCEDURES

Given the naturalistic nature of the study design, all participated patients will be diagnosed, treated, and monitored as in real clinical practice according to their physicians' judgement without additional interventions and procedures. Protocol-specified information relevant to CHB diagnosis and treatment will be collected from assessments generated from routine clinical care, including lab tests and medical records, complemented with investigators' evaluation at the entry of this study and thereafter at 6-month intervals for up to 3 years until the end of the study or until participant withdraws from this study. It is expected that diagnosis and treatment practice will vary across study hospitals and physicians.

Data will be collected using an innovative electronic approach, i.e. Smartphone App, with the intention to reduce the data collection burden on patients, investigators, and sites and also improve data collection efficiency and quality. The use of Smartphone App enables patients and investigators to upload lab tests and medical records and complete brief online evaluations (e.g. whether the patient remains on TDF? Any changes on TDF treatment?) via their smartphones.

There are no mandatory visits during the study period, however, according to the CHB clinical practice and CHB management guideline, CHB patients on anti-viral treatment should be monitored for at least every 6 months, e.g. HBV DNA, liver and renal function. Data collected and their timing are summarized in the SoA (See Section 2). The 6-month data collection interval is set to remind investigators to collect patient's data regularly. A minimal necessary medical evaluation in line with routine clinical practice following the guideline recommendation is required for all eligible patients at the entry of study for basic medical assessment on the basis of the judgement of treating physicians and willingness of patients. Other lab tests and procedures in the SoA will be judged by the treating physician and carried out by patients. Only available and identifiable assessments will be collected.

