All the lab test and procedures in the SoA will be performed based on the judgement of investigators/treating physicians and patients' willingness as in real-world practice. To achieve consistent evaluation of the effectiveness and safety of TDF treatment, the minimal essential lab test requested by CHB management guideline, including HBV DNA, eGFR and serum phosphate, will be performed in central lab during patients'

routine clinical visits. Other lab tests and procedures will be performed in local hospitals where patients seek care. Results will be collected by the innovative electronic approach.

CONFIDENTIAL

Supplementary central lab operation information would be provided in the accompanying study procedure manual (SPM). The SPM will provide the site personnel with administrative and detailed information on how to minimize the impact of the introduction of central lab to routine practice.

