9.3. Statistical Analyses

A detailed Reporting and Analysis Plan (RAP) outlining details of data analyses will be created and described below. Besides the 144-week analysis, key analyses may be conducted annually with the 48-week and 96-week cut-off data to look at short-term patient outcomes. No adjustment for multiplicity will be made for these analyses.

Continuous variables will be summarized for overall population and various subgroups using mean (standard deviation) and/or median (range), while categorical variables will be summarized in tables of frequencies and percentages. Comparative analyses will be performed across sub-groups using Student's t test or analyses of variance for quantitative variables, and Pearson's Chi-square test (Fisher exact test might be used when necessary) for qualitative variables. Nonparametric tests will be used when necessary.

In primary and secondary analyses, as this is a real-world study without mandatory scheduled visits, the assessments (e.g. lab test) may not be conducted exactly at 6-month intervals, but to keep the robustness of the estimation for effectiveness and renal function change, a time window that ± 28 days for week 48, 96 and 144 will be applied in each cut-off analyses. As the supportive analyses, the analyses with time windows that ± 3 months will be conducted. More details will be included in Reporting and Analyses Plan (RAP).

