9.3.2. Primary Analyses

In order to evaluate the effectiveness of TDF for the treatment of CHB patients, the following estimates will be summarized for the overall analysis population and subpopulations (e.g. gender, age group, clinical characteristics).

- The proportion of patients who achieve CVR at week of 144
- The proportion of patients who achieve CVR at weeks of 48 and 96
- The proportion of patients who achieve HBeAg loss and/or HBeAg seroconversion in HBeAg positive patients at weeks of 48, 96, and 144
- The proportion of patients who achieve HBsAg loss and/or HBsAg seroconversion at weeks of 48, 96, and 144
- The proportion of patients who achieve transaminase normalization at weeks of 48, 96, and 144

Sub-groups are defined according to patients sociodemographic, lifestyle and clinical characteristics and on treatment factors, including age, gender, baseline HBV DNA level, HBeAg status, baseline alanine aminotransferase level in relation to the upper limit of the normal range, receipt or no-receipt of previous treatment with other NUCs, previous history of drug resistance, baseline genotype, comorbidities (cirrhosis, hypertension, diabetes, renal disease), patient treatment adherence.

A time window that ± 28 days for week 48, 96 and 144 will be applied in each cut-off analyses. As the supportive analyses, the analyses with time windows that ± 3 months will be conducted.

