9.3.5. Other Analyses

Missing data is inevitable in this real-world study and can have an impact upon the interpretation of the data. In general, values for missing data will not be imputed unless otherwise specified. As this study takes a naturalistic approach, there will be no protocoldictated interventions or approaches to improve patient compliance besides what physicians do in practice. The study will use innovative electronic data capture approaches to increase the efficiency of data collection and reduce the effort on patients, physicians and sites, hopefully to reduce the chance of missing data.

The duration of patients on TDF, the reason for discontinuation if possible, and patients' adherence will be evaluated and recorded. Missing data issue will be explored in data analyses. For example, the reason and occurrence time of missing data will be summarized. It might be informative to know more the missing data and improve the adherence of treatment in the future.

When applicable, additional analyses may be conducted on primary, secondary, and exploratory objectives and research questions and will be described in RAP.

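### The ±28-day primary window, combined with discretionary testing, over-represents patients likelier to have an in-window test; CVR and renal proportions are biased if that chance depends on outcome

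*Protocol*

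**What the plan says.** Protocol section 9.3.2 fixes the primary window: "A time window that ± 28 days for week 48, 96 and 144 will be applied in each cut-off analyses". The wider one is supportive: "the analyses with time windows that ± 3 months will be conducted". Section 9.3 extends both to the renal outcomes, in a sentence that opens "In primary and secondary analyses, as this is a real-world study without mandatory scheduled visits".

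Testing is discretionary. Section 7 states "There are no mandatory visits during the study period" and describes tests as "performed based on the judgement of investigators/treating physicians and patients' willingness as in real-world practice". Section 5.1 says the same of the three central-laboratory tests, which "will be conducted in a central lab on the basis of the judgement of treating physicians and willingness of patients". The notes to the Schedule of Activities add: "Only available assessments will be collected from routine testing/evaluations". Section 7 cites guideline monitoring at least every 6 months and uses that interval as a reminder to investigators.

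On missing data, section 9.3.5 says: "In general, values for missing data will not be imputed unless otherwise specified". Section 9.2 admits to the main population anyone with baseline data and one post-baseline assessment. No section states the denominator of a week-48, week-96 or week-144 proportion.

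**The concern.** A 57-day window covers less than a third of a 6-month interval, so many patients who are on TDF and being followed may have no result inside it. Who has one depends on how often and when each patient is tested. If that is related to detectable HBV DNA or to a moving creatinine, the patients in the proportion are not a fair sample of those in follow-up.

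This affects the main CVR results and the renal proportions in section 9.3.3 (eGFR decline above 20%, confirmed low phosphate). It comes on top of losses from withdrawal, and the stated precision does not reflect it.

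**Working it through.** **1. The plan's own figure.** Inputs from sections 9.1.2 and 9.1.3: N = 2000, attrition 35%, CVR 80%. Completers: 2000 × 0.65 = 1300. Half-width: 1.96 × √(0.8 × 0.2 / 1300) = 0.0217. The stated 2.2% reproduces, but only if every completer has a usable week-144 value.

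**2. Window against schedule.** One month is taken as 30.44 days.

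| Target | ±28-day window (days) | 6-month mark | Miss if tested exactly on the mark |
|---|---|---|---|
| Week 48 | 308–364 | month 12, day 365 | about 1 day |
| Week 96 | 644–700 | month 24, day 730 | about 30 days |
| Week 144 | 980–1036 | month 36, day 1096 | about 60 days |

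A patient tested exactly on schedule misses all three windows, so off-schedule patients supply the data.

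**3. Capture and precision.** Assumption: test dates fall at random relative to the window. P(in-window test) = 57 / interval, so 57 / 182.6 = 31% for 6-monthly and 57 / 91.3 = 62% for 3-monthly testing. At 31%, 1300 × 0.312 ≈ 406 patients contribute, and 1.96 × √(0.16 / 406) = 0.039.

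**4. Bias in CVR.** Let r be the ratio of in-window testing probabilities, responders to non-responders. On complete cases, observed = 0.8r / (0.8r + 0.2).

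| r (assumed) | 0.5 | 0.8 | 0.9 | 1.0 | 1.1 | 1.25 | 2 |
|---|---|---|---|---|---|---|---|
| Observed CVR | 66.7% | 76.2% | 78.3% | 80.0% | 81.5% | 83.3% | 88.9% |

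For a 2.2-point bias, solve r = [x / (1 − x)] × 0.2 / 0.8. With x = 0.778, r = 0.876. With x = 0.822, r = 1.154.

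**5. Bias in a renal proportion.** The same formula applies with an assumed true event rate of 5%. If event patients are twice as likely to have an in-window test, observed = 0.05 × 2 / (0.05 × 2 + 0.95) = 9.5%. If they are half as likely, it is 2.6%.

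**6. Does ±3 months solve it?** Left at week 144, the window runs from about day 917 to day 1099. The month-30 mark (day 913) and month-36 mark (day 1096) sit at its edges, so with scattered visits each falls inside about half the time. A 6-monthly tester is captured with probability about 1 − 0.5 × 0.5 = 75%. Simulation with normal scatter of SD 15 to 60 days (200,000 patients per setting) agrees; the ±28-day week-144 window captures 0–23% of the same patients. If non-responders are tested 3-monthly and nearly all captured, observed CVR = 0.8 × 0.75 / (0.8 × 0.75 + 0.2) = 75%.

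Simulated observed CVR for the same contrast (responders 6-monthly, non-responders 3-monthly), centred on month 36:

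| Window | SD 30 days | SD 45 days | SD 60 days |
|---|---|---|---|
| ±28 days | 79.7% | 77.4% | 74.0% |
| ±3 months | not needed | 79.5% | 78.4% |

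Both width and centre therefore matter.

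**The case against.** The strongest reply has four parts.

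- **The denominator is not stated.** A reader might infer that the protocol restricts the proportions to patients with an in-window test. It does not say so: estimates are for the overall analysis population, and further window detail is deferred to the Reporting and Analysis Plan. This stands as a limit on the claim. It does not remove the problem: if untested patients counted as failures, CVR would be understated instead (0.8 × 0.31 ≈ 25% at the capture in step 3).
- **Outcome-dependent testing is an assumption.** No document says that non-responders are tested more often or less often. Closer monitoring of detectable virus would lower observed CVR; poor attendance by non-responders would raise it. This stands.
- **Visits are likely to cluster at the 6-month reminders.** A reader might take 66.7%, 88.9% or 9.5% as expected results. They illustrate a twofold contrast, which step 3 produces only with randomly timed dates. With clustered visits and a window centred on month 36, bias is negligible at an SD of 30 days or less, so much of the harm comes from the misalignment in step 2. This stands, and it is why the fix must move the centre as well.
- **Safeguards exist.** The ±3-month analysis is planned. Section 9.3.5 summarises reasons for and timing of missing data, section 9.3.3 has mixed models for mean eGFR and phosphate change, and section 9.3.4.2 has a mixed model for CVR if data permit. None corrects the primary proportions: the first is supportive and off-centre, the second describes, the third concerns means, and the fourth is exploratory.

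That this is merely left to the analysis plan does not hold. The protocol itself chooses which window is primary and sets the default on imputation.

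**Conclusion.** The point holds conditionally. A 57-day primary window, discretionary testing and default non-imputation are all in the text. On a complete-case reading they over-represent patients likelier to have an in-window test, and the CVR and renal proportions are biased if that chance depends on outcome.

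The size cannot be computed from the documents. At a true CVR of 80%, a testing ratio below about 0.88 or above about 1.15 is enough to exceed the planned 2.2 points. Separately, the 2.2% presumes full capture among 1300 completers; under random dates and 6-monthly testing it becomes about 3.9%.

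Two stronger readings are not supported. One is that every proportion is certainly biased, or biased in a known direction: that needs testing rates the protocol does not give. The other is that frequent testers are counted more than once: each patient enters a proportion once, so they are at most over-represented. The change should be made, but the point does not invalidate the study.

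**What to change.** - Make the primary value, for each patient, the single assessment nearest the target within ±3 months, with the target at months 12, 24 and 36 to match the collection schedule. Swapping the two windows while leaving them at weeks 48, 96 and 144 is not enough (step 6).
- Keep ±28 days as the supportive analysis.
- State the denominator of each proportion and how a patient with no in-window value is handled.
- Report the share with an in-window value by last known HBV DNA and eGFR status.
- If those shares differ, add a sensitivity estimate weighted by the inverse probability of being assessed.

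The cost is small: both window widths are already planned, so the additions are a re-centring, one table and one conditional analysis. The downside is that some values lie up to 3 months from the target. Because follow-up is described as 3 years, the text should also say whether a late month-36 test is still collected; otherwise the upper half of that window would be empty.

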9.3.3. Secondary Analyses

Patients' renal functional change during TDF treatment period will be explored.

- The proportion of patients whose eGFR (MDRD equation) decline >20% from baseline at weeks of 48, 96 and up to week 144 will be summarized for the overall study analysis population and sub-group populations.
- Mean and 95% confidence intervals for the change from baseline in eGFR values will be calculated for the overall analysis population, as well as for the subpopulations of interests. A mixed effect model will be fitted to explore the impacts on the mean change from baseline in eGFR of fixed effects of age, gender, treatment-naïve or experienced, ADV or non-ADV, type of baseline comorbidities (Cirrhosis, Hypertension, diabetes mellitus (DM), non-overlapping), baseline eGFR values, baseline HBV-DNA counts, baseline HBeAg status, and other factors as appropriate, and random effects of subject ID.
- The percentage of change from baseline in eGFR will be estimated for the overall analysis population and by sub-populations at weeks 48, 96, and 144. Figures of mean eGFR values overall and the sub-populations of interests will be generated.
- The proportion of patients with confirmed a serum phosphate Grade 3 or 4 abnormality (<2.0 mg/dL) at weeks of 48, 98 and 144 will be summarized for the overall study analysis population and sub-group populations.
- The percentage of change from baseline in serum phosphate will be estimated for the overall analysis population and by sub-populations at weeks 48, 96, and 144. Figures of mean serum phosphate values overall and the sub-populations of interests will be generated.
- Mean and 95% confidence intervals for the change from baseline in serum phosphate values will be calculated for the overall analysis population, as well as for the sub-populations of interests. A mixed effect model will be fitted to explore the impacts on the mean change from baseline in serum phosphate of fixed effects of age, gender, treatment-naïve or experienced, ADV or non-ADV, type of baseline co-morbidities (Cirrhosis, Hypertension, DM, non-overlapping), baseline eGFR values, baseline HBV-DNA counts, baseline HBeAg status, baseline phosphorus and other factors as appropriate, and random effects of subject ID.

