The effectiveness and renal safety results of TDF varies between registered clinical trials [complete virological response (CVR) over 95%] and real-world research (CVR approximately 71 to 92%) [Pol, 2012, Idilman, 2015, Kim, 2015], partly due to the difference between clinical trial patient population and real world study population. Phase III clinical trials are conducted under well-controlled conditions among pre-selected patients with strict in/exclusion criteria, generally eliminating older patients and those with co-infections or comorbidities (such as cirrhosis). Compared with most patients seen in real world practice, those participating in clinical trials are typically younger and healthier with less comorbidity and better treatment adherence. Understanding how antivirals perform in real world general patient population is more important to guide routine clinical practice. The results from high-quality real-world cohorts will continue to provide clinical guidance for physicians by providing safety and effectiveness evidence across diverse treatment settings and in a broader array of patients and enable more patients to benefit from the available treatment options.

Lampertico et al. [Lampertico, 2016] reviewed recent real-world evidence on the safety of TDF treatment among HBV-monoinfected patients. Overall, TDF can lead to minor reduction in eGFR and BMD, which was mainly observed during early stage of treatment and remained stable in long-term follow up in most patients. Although TDF was well tolerated with no clinically significant renal toxicity, evidence from cohort studies seems to be conflicting. Reductions in GFR/Creatinine among HBV patients treated with TDF were reported, the clinical significance of these changes needs more discussion and the degree of association between TDF and changes in renal function indicators varies across studies. The inconsistency might result from small sample size, different baseline population with different renal function, varying measures of renal function. Few studies observed BMD during TDF treatment among CHB patients. Gill et al. carried out a single-centre cohort study in the UK, specifically to assess the impact of TDF on BMD in 170 HBV-monoinfected patients. There was no difference in T-score between treatment groups for lumbar or femoral neck measures, but TDF was associated with a lower hip T-score compared with no TDF (P = 0.02) [Gill, 2015].

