7.3. Follow Up Data Collection

Study participants will be followed up for 3 years or until they withdraw from the study. Follow-up information will be collected at 6-month intervals:

- Regular tests
 - o HBV serology
 - o HBV DNA
 - o Serum creatinine and eGFR [MDRD equation]
 - Serum phosphate
 - Alanine transaminase (ALT) and aspartate transaminase (AST)
- Other tests and procedures
 - o AFP
 - o Hepatic ultrasound
 - Genotype
 - o Bone mineral density

- Liver biopsy
- o Transient elastography (fibrotouch or fibroscan)
- Hepatic ultrasound /computed tomography (CT) /magnetic resonance imaging (MRI)
- Updated CHB treatment details, e.g. any change to regimen or dosage and reason for change
- Comorbidity and concomitant medication review
- Spontaneous AEs if available
- For treatment adherence, it will be evaluated by the treating physician according to the patients' care seeking care, e.g. whether take the medication as prescribed, have you ever discontinued your medications and for how long?
- For participants who discontinue TDF prematurely, duration of treatment and reasons for TDF discontinuation will be recorded, e.g. SAEs, non-SAEs, and insufficient effectiveness.

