8.2. Withdrawal from the Study

A participant may withdraw from the study at any time at his/her own request, or may be withdrawn at any time at the discretion of the investigator for safety, behavioral, compliance or administrative reasons. If the participant withdraws consent for disclosure of future information, the sponsor may retain and continue to use any data collected before such a withdrawal of consent.

In this real-world study, participants will be considered withdrawal from the study if any of the following events occurs within the 3-year study period:

Discontinuation of TDF (Viread, Beixin or Naxinde) for at least 28 days

Participation in clinical trials for any new drugs not limited to CHB-related ones during the 3-year study period

Study closed/terminated

Withdrew consent

The overall duration of TDF treatment and the reason for discontinuation of TDF treatment will be collected and the patient's adherence will be evaluated by the investigator a designed questionnaire.

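### Every renal result with a named time point sits at weeks 48, 96 and 144, so the scheduled month 6, 18 and 30 values fall outside the stated windows and their use elsewhere is left open

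*Protocol*

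**What the plan says.** **Collection.** Section 7.3 states: "Follow-up information will be collected at 6-month intervals". The Schedule of Activities (section 2) lists creatinine/eGFR and phosphate at months 6, 12, 18, 24, 30 and 36.

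**Renal results with named weeks.**
- Section 9.3.3: the "percentage of change from baseline in eGFR will be estimated for the overall analysis population and by sub-populations at weeks 48, 96, and 144". Percentage change in phosphate and the proportion with phosphate below 2.0 mg/dL follow the same pattern.
- The large-decline proportion has slightly looser wording: "decline >20% from baseline at weeks of 48, 96 and up to week 144 will be summarized".
- The absolute change in eGFR and in phosphorus has no week in section 9.3.3. Table 2 in section 4 places both at weeks 48, 98 and 144. Several lines print 98 where others print 96.

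**Windows.** For primary and secondary analyses, section 9.3 says "a time window that ± 28 days for week 48, 96 and 144 will be applied in each cut-off analyses". It names renal function change among the reasons, adds supportive windows of ±3 months and leaves further detail to the RAP.

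**Renal analyses with no time restriction where they are described.** These are the two mixed models with a random subject effect, the figures of mean eGFR and mean phosphate, and the creatinine, creatinine clearance and phosphate summary in section 9.3.4.4. Neither mixed model lists a visit or time term, though both allow other factors.

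**Who stays under observation.** One of the withdrawal events in section 8.2 is: "Discontinuation of TDF (Viread, Beixin or Naxinde) for at least 28 days". Section 9.3.5 says missing values are in general not imputed. Section 9.2 admits a patient to the main population with the requested baseline data and one post-baseline assessment.

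**The concern.** The secondary objective is renal change during TDF treatment. The protocol's own background puts the expected fall early. Section 3.2 describes a minor reduction in eGFR and BMD "which was mainly observed during early stage of treatment and remained stable in long-term follow up in most patients", and it cites a Taiwanese study whose largest fall was in year 1 (96.0 to 88.3, a mean drop of 7.7).

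The time-pointed results nevertheless begin at the week-48 window. A patient whose eGFR falls at month 6, who then stops TDF and is withdrawn, belongs to the analysis population but has no value in any named window. The renal proportions and mean changes then describe those who stayed. If leaving is related to renal function, the results look better than the treated cohort's experience. Adverse events are collected only as spontaneous reports (section 7.4), so the scheduled laboratory tests are the systematic source of renal information.

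**Working it through.** **1. The plan's attrition figure.** Section 9.1.2 assumes 35% loss to follow-up and discontinuation: 2,000 × 0.65 = 1,300 completers. The half-width is 1.96 × √(0.80 × 0.20 / 1,300) = 0.0217, which matches the stated 0.022. The 35% is used in step 4.

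**2. Windows in days.** Window = 7 × week ± 28 days, or ± 3 months (3 × 365.25/12 = 91.3 days).

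| Week | Centre | ±28 days | ±3 months |
|---|---|---|---|
| 48 | 336 | 308–364 | 244.7–427.3 |
| 96 | 672 | 644–700 | 580.7–763.3 |
| 144 | 1008 | 980–1036 | 916.7–1099.3 |

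**3. Where the intermediate visits fall** (one month = 30.44 days).

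| Visit | Nominal day | In a ±28-day window? | In a ±3-month window? | Delay needed to reach the next supportive window |
|---|---|---|---|---|
| Month 6 | 182.6 | No | No | 244.7 − 182.6 = 62.1 days |
| Month 18 | 547.9 | No | No | 580.7 − 547.9 = 32.8 days |
| Month 30 | 913.1 | No | No | 916.7 − 913.1 = 3.6 days |

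With 28-day months the visits fall on days 168, 504 and 840, again outside every window. Visit dates are not fixed in this study, so a slightly late month-30 test would enter the supportive analysis. A month-6 test would have to be about two months late.

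**4. Patients who leave between month 6 and the first window.** Assume the 35% accrues at a constant rate to day 1008 (the documents give no time course). The proportion remaining at day d is S(d) = 0.65^(d/1008).

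- S(183) = 0.9248, S(245) = 0.9006, S(308) = 0.8767.
- Before the main window opens: S(183) − S(308) = 0.0481; × 2,000 ≈ 96 patients.
- Before the supportive window opens: S(183) − S(245) = 0.0242; × 2,000 ≈ 48 patients.

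For these patients, month 6 is the only scheduled post-baseline renal value. On the same assumption, S(548) − S(644) = 0.0318 (about 64 patients) leave between month 18 and the week-96 main window, and S(913) − S(980) = 0.0191 (about 38) between month 30 and the week-144 main window. These later leavers may have a value in an earlier window, but their latest one falls outside.

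**5. What week 48 can and cannot show.** Change is measured from baseline. A fall at month 6 that persists is therefore still present in the week-48 value. A fall that has recovered by then is not, and neither is any fall in a patient who has already left.

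**The case against.** **A reader might infer that the month 6, 18 and 30 values enter no estimate and that half the renal data are discarded.** The protocol does not say so. The mixed models, the figures and the section 9.3.4.4 summary carry no time restriction where they are described, and the large-decline bullet is worded up to week 144. The window rule defines which values count for weeks 48, 96 and 144; it does not order other values to be dropped. Time to first CVR needs values between those weeks, so the windows cannot govern every analysis. This stands: use of the intermediate values in the models and figures is unspecified, not excluded. Section 9.3 and Table 2 can still be read the narrower way.

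**A reader might infer that eGFR loss before week 44 is invisible.** That does not follow either. Persisting loss shows at week 48, the supportive window opens at about week 35, and the pattern cited in section 3.2 is an early fall followed by stability. The cited year-1 fall also spans the week-48 window.

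**Patients who stop are not wholly unrecorded.** Reasons for discontinuation are collected and spontaneous adverse events reported. This stands, but neither source supplies a measured eGFR or phosphate change for the renal results.

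**Annual summaries match the stated objectives, and visit selection is RAP content.** This stands in part. Annual headline points are reasonable. But the protocol itself has fixed the weeks and windows, so a RAP that follows them faithfully would reproduce the gap in the time-pointed results.

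**Conclusion.** The point holds for the renal results with a named time point: decline above 20%, percentage and absolute change in eGFR and phosphate, and phosphate below 2.0 mg/dL. All sit at weeks 48, 96 and 144, and the scheduled month 6, 18 and 30 values fall outside both sets of windows at nominal dates. Whether those values enter the mixed models and figures is open.

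What is missed is loss that recovers and loss in patients who leave before the window opens. The number exposed to the second problem is about 96 of 2,000 for the main analysis, or about 48 for the supportive one. Both figures rest on constant attrition: losses concentrated soon after month 6 would raise them, later losses would lower them. They also assume that a month-6 test was done, which the study does not require, and they ignore the up to 10% of patients already on TDF at entry.

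The share of these leavers with renal decline is unknown, and the 35% covers every reason for leaving. A reader might infer a count of missed renal cases and set it beside the rates cited in section 3.2 (nearly 1%, and at most 2.2%). The documents do not support that: those rates are adverse events over long follow-up, a different outcome, and any count would come from an assumed share. The direction of selection is plausible, but its size cannot be given.

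**What to change.** In section 9.3.3:

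- Add months 6, 18 and 30, each with its own stated window, to the eGFR and phosphate summaries and figures, including the proportions with decline above 20% and with phosphate below 2.0 mg/dL.
- State that both mixed models use all 6-monthly post-baseline values and include a visit or time term.
- Keep weeks 48, 96 and 144 as the headline time points.

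The cost is protocol and RAP wording and a few more table columns. No new visit, test or patient is needed. One limit remains: the change cannot recover patients who leave before month 6, about 2,000 × (1 − 0.9248) = 150 under the same constant-rate assumption. The number contributing at each time point should therefore be shown beside each renal result.
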